RESEARCH QUESTION	Does Parkinson's Disease Inpatient Clinical Knowledge and Management Program and the WatchRx System make a difference in the clinician knowledge, customized PD order time and PD medication administration time, complications (administered contraindicated medication, falls, positive delirium scores, and positive confusion), medication error and length of stay during hospitalization?
HYPOTHESIS	
Ho1:
 
Parkinson's Disease Inpatient Clinical Knowledge and Management Program will not make a difference in the clinician knowledge.
 
Ha1:
 
Parkinson's Disease Inpatient Clinical Knowledge and Management Program will make a difference in the clinician knowledge.
 
Ho2:
 
Parkinson's Disease Inpatient Clinical Knowledge and Management Program will not make a difference in the customized PD order time and PD medication administration time, complications (administered contraindicated medication, falls, positive delirium scores, and positive confusion), medication error and length of stay during hospitalization.
 
Ha2:
 
Parkinson's Disease Inpatient Clinical Knowledge and Management Program will make a difference in the customized PD order time and

Protocol Synopsis	
	
PD medication administration time, complications (administered contraindicated medication, falls, positive delirium scores, and positive confusion), medication error and length of stay during hospitalization.
 
Ho3:
 
WatchRx System will not make a difference in the customized PD order time and PD medication administration time, complications (administered contraindicated medication, falls, positive delirium scores, and positive confusion), medication error and length of stay during hospitalization.
 
Ha3:
 
WatchRx System will make a difference in the customized PD order time and PD medication administration time, complications (administered contraindicated medication, falls, positive delirium scores, and positive confusion), medication error and length of stay during hospitalization.

STUDY DESIGN	
Two Part Study Design
 
 
• Part 1: Retrospective Phase
 
• Part 2: Prospective Phase
 

INTERVENTION	Clinician Education Program, WatchRx system, and enrollment in PD registry.
SAMPLE SIZE	
Patients - 300 in total
 
150 - retrospective phase
 
150 - prospective phase

PRIMARY OBJECTIVES	To measure the difference in knowledge of the clinicians before and after completing the Parkinson's Disease Inpatient Clinical Knowledge and Management Program.
PRIMARY ENDPOINTS	Difference in PD Knowledge assessment score before and after Parkinson's Disease Inpatient Clinical Knowledge and Management Program (Appendix I A PD Knowledge assessment score)

Protocol Synopsis	
SECONDARY OBJECTIVES	
 
1. To measure the difference that the Parkinson's Disease Inpatient Clinical Knowledge and Management Program has on PD medication administration time, administered contraindicated medication, PD medication errors, falls, positive confusion, positive delirium scores, and length of stay for PD patients.
 
2. To measure the difference that the WatchRx system has on PD medication administration time, administered contraindicated medication, PD medication errors, falls, positive confusion, positive delirium scores, and length of stay for PD patients.
 

SECONDARY ENDPOINTS	
 
• Difference in scheduled versus actual PD medication administration time
 
• Number of medication errors
 
• Number of contraindicated medications administered
 
• Number of falls
 
• Number of positive confusion scores
 
• Number of positive delirium scores
 
• Length of stay
 

STUDY PERIOD	
Retrospective Data Period: January – June 2015
 
Prospective Data Period: After the clinicians have completed the Parkinson's disease Inpatient Clinical Knowledge and Management Program and the WatchRx Smartwatch is integrated in the medication administration for PD medications.

SPONSOR	Hackensack University Medical Center
STATISTICAL ANALYSIS PLAN, DATABASE, DATA ENTRY & ANALYSES	
[name]  Hackensack University Medical Center  Research Biostatistician  Department of Research  Office: [contact]  [contact]  Email: [contact]

**Statement of Investigator**

# **Parkinson's Disease Inpatient Clinical Knowledge and management**

*An observational, quasi-experimental retrospective and prospective study.*

### STUDY SPONSOR

Hackensack University Medical Center  
[name]  
[name]

---

Definitions	
Discrete data	Data with numerical value that is distinct and separate
MDR	The Multidisciplinary (MDR) is the clinical infrastructure supporting a multidisciplinary/interdisciplinary framework for clinical practice promoting a patient-centered, evidence- and value-based care within a managed care environment
Dementia Assessment Method	Standardized examination used to detect dementia (Mini-Cog)
Delirium Assessment	Standardized examination used to detect delirium (CAM).
Unstructured data	Unstructured Data (or unstructured information) refers to information that either does not have a pre-defined data model or is not organized in a pre-defined manner. Unstructured information is typically text-heavy, but may contain data such as dates, numbers, and facts.

## Introduction and Background

Parkinson's Disease (PD), the second-most common neurodegenerative disorder after Alzheimer's disease is a progressive disorder of the central nervous system affecting movement resulting in tremor of the hands, arms, legs, jaw, face, bradykinesia, rigidity of limb, trunk/postural instability, impaired balance and coordination (Kowal, Dall, Chakrabarti, Storm, and Jelin, 2013).

PD prevalence rate in the United States is estimated to be approximately 0.3% (Kowal et al., 2013) and is ranked the fourteenth leading cause of death (CDC, 2013). Depending on the methodology, the national prevalence data on PD is varied and insufficient (McLaughlin, Piryatinsky, Epstein-Lubow, Marino, and Friedman, 2014). PD is projected to increase by 4% to 5% in age 65 and over 85 years respectively (Weintraub, Comella, and Horn, 2008), and is associated with high economic burden exceeding \$14.4 billion per year (Kowal et al. 2013).

Admission to the hospital is identified as a major risk factor due to imprecise timing of medication administration, disruption of sleep pattern, dietary changes, and unfamiliarity of the hospital environment, which all contribute to exacerbation of PD symptoms (Oguh & Videnovic, 2012; Parkinson's disease Foundation, 2015). Exacerbation of PD symptoms is also associated with higher risk for falls and falls with injury during hospitalization. A study by Chou et al., (2011) involving 51 worldwide National Parkinson Foundation Centers found 94% of centers were not confident in the care and knowledge hospital professionals provided specific to: PD medications, complex drug interactions, contraindications and precise timing of medication administration. A survey on medication administration in PD patients found 75% of hospitalized patients failed to receive their medications on time (Okun, 2010), thus compromising patient care. According to Chou et al. (2011), Martignoni et al. (2004), Michigan Parkinson Foundation

(2013) hospital co-morbidities could be improved or prevented by adjustment of PD medication and medication adherence, critical in decreasing hospital length of stay. In general, the length of stay for patient with PD is 1.45 times higher (Dorsey et al., 2005; McLaughlin et al., 2014) in comparison to non- PD patients.

PD prevalence is projected to double over the next few decades as the size of the elderly population increases. This projected growth and anticipated demographic burden has created the impetus for Hackensack University Medical Center PD Management Team to create new innovative strategies incorporating current best practices and protocols for delivering care and treatment during hospitalization in this subset of patient population.

## **Study Purpose and Rationale**

It is documented that PD patients are more likely to experience complications during hospitalization (Chou et al., 2011; Gerlach et al., 2012). A preponderance of the evidence indicate decrease motor function increases the risk for falls and falls with injury, decline in mental capacity, the failure to detect depression, and lack of knowledge and expertise on the care of PD patients by health care professionals are all contributors leading to the exacerbation of complications during acute hospitalization (Ashslok, 2014; Gerlach, Broen, Dombury, Vermeij, & Weber 2012; Mondolo, Jahanshahi, Grania, Biasutti, Cacciatori & Benedetto, 2006). The root cause of the failure to meet the specific therapeutic requirements and overall care needs of PD patients during hospital stay is related to failure of health care clinicians to implement current evidence-based Parkinson's specific disease care guidelines (Gerlach et al., 2012; Skelly et al., 2014).

The complexity of PD coupled with the absence of Parkinson specific core knowledge on the care of these patients by frontline clinicians ( Gerlach et al, 2012; Thompson, 2015) has led to the status quo of prolonged length of stay (Braga, Pederzoli, Antonini, Beretta, Crespi, 2014; Ramirez et al. 2015) , deterioration of PD disease symptoms (Ahlskog, 2014; Gerlach, 2012), increased psychological and physical morbidity (Soundy, Stubbs, and Roskell, 2014) and subsequent reduction in quality of life (Duncan et. al (2014). Timely administration of PD improves morbidity, mortality and length of stay (CMS 2014).

While the goal during hospitalization is to provide, safe and effective high quality care. 74% of PD patients receive incorrect medications (Martinez-Ramirez et al, 2015 and are at increased risk for developing complications related to medication administration. According to the Institute for Safe Medication Practices [ISMP] (2015 p. 19) “patients with PD require strict adherence to an individualized timed medication regimen of anti-parkinsonian agents.” Medications must be administered on time, based on the patient’s unique schedule. A comprehensive search of the literature from 2009 – 2015 found few studies evaluating the impact of focused integrated inter and multidisciplinary approach to managing PD patients during hospitalization. In another survey, PD patients’ perceptions is that hospital staff lacked understanding of PD, the importance of medication timeliness, and appreciation of valuable insights from patients, families and caregivers (Oguh & Videnovic, 2012).

A paradox of the U. S. healthcare system is that it leads the world in medical science and technology, yet there is limited application of technology to enhance patient-centered care in the hospital setting. In accordance with the Institute of Medicine’s (2001) quality performance goals, safety, effectiveness, timeliness, patient-centeredness, efficacy and equity, this study will integrate WatchRx system, a medication reminder system. The WatchRx system includes a

smartwatch, caregiver app and online web interface which allows clinicians to customize the medication administration time and alerts the patient and the nurse when the medication to be administered.

This study will conduct research on establishing multidisciplinary clinical guidelines in management of PD across the acute care setting. We will further explore the impact of PD medication management on patients hospital length of stay and complications associated with mismanagement. We intend to create a PD registry for Hackensack University Medical Center, and possibly expand across the Hackensack Meridian Health Network in the future. According to the New Jersey Assembly Bill 2955, December 2014, patients and/or their designated caregiver must receive discharge instructions prior to discharge from the hospital and appropriate referrals for follow-up care. This study aligns New Jersey Bill 2955 (2014) mandating the education and preparation of designated caregiver in the discharge plan of care of hospitalized PD patients.

## **Research Question**

Does Parkinson's Disease Inpatient Clinical Knowledge and Management Program and the WatchRx System make a difference in the clinician knowledge, customized PD order time and PD medication administration time, complications (administered contraindicated medicationfalls, positive delirium scores, and positive confusion), medication error and length of stay during hospitalization?

## **Hypothesis**

Ho1:

Parkinson's Disease Inpatient Clinical Knowledge and Management Program will not make a difference in the clinician knowledge.

Ha1:

Parkinson's Disease Inpatient Clinical Knowledge and Management Program will make a difference in the clinician knowledge.

Parkinson's Disease Inpatient Clinical Knowledge and Management Program will not make a difference in the customized PD order time and PD medication administration time, complications (administered contraindicated medication, falls, positive delirium scores, and positive confusion), medication error and length of stay during hospitalization.

Ha2:

Parkinson's Disease Inpatient Clinical Knowledge and Management Program will make a difference in the customized PD order time and PD medication administration time, complications (administered contraindicated medication, falls, positive delirium scores, and positive confusion), medication error and length of stay during hospitalization.

Ho3:

WatchRx System will not make a difference in the customized PD order time and PD medication administration time, complications (administered contraindicated medication, falls, positive delirium scores, and positive confusion), medication error and length of stay during hospitalization.

Ha3:

WatchRx System will make a difference in the customized PD order time and PD medication administration time, complications (administered contraindicated medication, falls, positive

delirium scores, and positive confusion), medication error and length of stay during hospitalization.

## **Primary Objective**

To measure the difference in knowledge of the clinicians before and after completing the Parkinson's Disease Inpatient Clinical Knowledge and Management Program.

## **Primary Endpoints**

Difference in PD Knowledge assessment score before and after Parkinson's Disease Inpatient Clinical Knowledge and Management Program (Appendix A- PD Knowledge assessment score).

## **Secondary Objectives**

1. To measure the difference that the Parkinson's Disease Inpatient Clinical Knowledge and Management Program has on PD medication administration time, administered contraindicated medication, PD medication errors, falls, positive confusion, positive delirium scores, and length of stay for PD patients.
2. To measure the difference that the WatchRx system has on PD medication administration time, administered contraindicated medication, PD medication errors, falls, positive confusion, positive delirium scores, and length of stay for PD patients.

## **Secondary Endpoints**

- Difference in scheduled versus actual PD medication administration time
- Number of medication errors

- Number of contraindicated medications administered
- Number of falls
- Number of positive confusion scores
- Number of positive delirium scores
- Length of Stay

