## **Retrospective Study Period**

Version 5 Revised 5/9/2019

Data collection of adult patients admitted with a primary and secondary diagnosis of Parkinson's disease during January – June 2015.

- Data will be extracted from the EPIC (current EMR system at Hackensack University Medical Center).
- Business intelligence will run the data and create reports with the specific data points mentioned above prior to providing it to the study team for further statistical analysis.

Data collected from the automatic dispensing cabinet barcoding database will verify accuracy and timeliness of medication.

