#### **WatchRx System Enrollment:**

Using Internet Explorer web browser, the Principal Investigator and the TC Pharmacist (sub investigator(s) will complete the following:

- Enter the patient's information into the WatchRx Inc. Website interface to create the patient profile and PD medication regimen
- Register the patient into WatchRx web interface via website URL by entering the PD patient's name, unit number and room number.

- Enter the patient PD medication administration schedule as ordered
- Assign the WatchRx Smartwatch to the patient
- Review the WatchRx Smartwatch functions with the patient
- Review the Aware in Care Kit with the PD patient

The primary nurse will be asked to wear the WatchRx smartwatch. After obtaining verbal consent, the Principal Investigator and TC Pharmacist will review the patient's PD medication schedule in WatchRx smartwatch with the primary nurse.

The WatchRx web interface will activate reminder alerts from the patient's WatchRx Smartwatch to the primary nurse WatchRx smartwatch. Alerts reminders will send fifteen minutes before the PD medication is due. Medication reminder alerts will continue to be sent from WatchRx smartwatch worn by the patient to the WatchRx Smartwatch worn by primary nurse at 3-minute intervals for a period of 10 minutes or until the PD medication is administered.

At each end-of-shift and/or at handoff, the WatchRx smartwatch will be cleaned using Super SaniClothTM and the nurses will document completion of the WatchRx smartwatch cleaning procedure on the WatchRx Smartwatch cleaning log and verify by signing their names (Appendix F).

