## Data Analysis

The summary of the demographic characteristics will be presented. Continuous variables will be summarized using mean (SD) or median (interquartile range) depending on whether or not the data follow the normal distribution. Categorical variables will be summarized by frequency (percentage). Comparison of continuous variables between any independent groups will be examined using two-sided t-test or two-sided Wilcoxon rank sum test, analysis of variance (ANOVA) or Kruskal-Wallis test followed by pairwise tests, as appropriate. Categorical variables will be examined using Fisher's exact test or Pearson's Chi-square test, as appropriate.

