## **Benefits**

This study will improve timely administration of medications to PD patients. Patients enrolled in the study will have direct monitoring of their medication compliance and adherence. This study will improve knowledge of Parkinson's disease amongst clinicians and better medication management of PD patients.

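### The timing endpoint does not say signed or absolute; analysed as a signed difference, on-time doses given earlier could look like better timeliness with no fewer late doses

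*Combined protocol and SAP*

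**What the plan says.** The Synopsis and Secondary Endpoints define the timing outcome only as "Difference in scheduled versus actual PD medication administration time". Neither place says whether the difference is signed or absolute, how early doses count, or how a patient's several doses are combined. Data Analysis gives a general rule: "Comparison of continuous variables between any independent groups will be examined using two-sided t-test or two-sided Wilcoxon rank sum test".

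The device description under WatchRx System Enrollment says "Alerts reminders will send fifteen minutes before the PD medication is due", with repeats "at 3-minute intervals for a period of 10 minutes or until the PD medication is administered". Study Purpose and Rationale says the system "alerts the patient and the nurse when the medication to be administered".

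The aim is timeliness. The Introduction cites a survey that "found 75% of hospitalized patients failed to receive their medications on time", and Benefits states: "This study will improve timely administration of medications to PD patients".

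Material for a sharper definition is already in the protocol. Both study-period sections state: "Data collected from the automatic dispensing cabinet barcoding database will verify accuracy and timeliness of medication". The Appendix E education sheet sets an on-time limit of 30 minutes. The endpoint refers to neither. Number of medication errors is a separate endpoint, but it is undefined, so it is unclear whether it counts a late dose.

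**The concern.** The default way to compute a difference between two times is to subtract one from the other. In a mean of such differences, a dose 10 minutes early cancels 10 minutes of another dose's lateness. For many interventions this would be a minor looseness. Here the intervention itself may push doses early, because the first reminder comes 15 minutes before the due time.

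Doses that were already on time could therefore move a few minutes earlier and lower the signed mean, whether or not any late dose is corrected. The signed mean cannot separate fewer late doses from on-time doses given slightly sooner, and only the first answers the problem set out in the Introduction. The outcome is one of seven secondary endpoints, but it is the one closest to how WatchRx is meant to work.

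**Working it through.** **Plan's own figure.** There is none to reproduce. The 300 patients are a convenience sample, and the plan states no SD, effect size or power for timing.

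**Inputs.** From the documents: 150 patients per phase, and reminders starting 15 minutes before the due time. Assumed: one dose per patient; a share p of doses late by 45 minutes in both phases; all other doses at the due time before the intervention and s minutes early after it.

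**Formulas.**
- Fall in signed mean = (1 − p) × s
- SD before = 45 × √(p(1 − p)); SD after = (45 + s) × √(p(1 − p))
- SE = √((SD before² + SD after²) / 150); z = fall / SE
- Rise in mean absolute deviation = (1 − p) × s
- Change in late share = 0 by construction

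**Worked case, p = 0.25, s = 10.** The signed mean goes from 0.25 × 45 = 11.25 to 11.25 − 7.5 = 3.75 minutes. The SDs are 19.49 and 23.82, SE = √((19.49² + 23.82²) / 150) = 2.51, and z = 7.5 / 2.51 = 2.99. Absolute deviation worsens from 11.25 to 18.75 minutes. The late share stays at 25%.

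**Range.**

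| Late share | Shift (min) | Fall in signed mean (min) | SE | z |
|---|---|---|---|---|
| 15% | 5 | 4.25 | 1.96 | 2.17 |
| 15% | 10 | 8.50 | 2.07 | 4.10 |
| 25% | 5 | 3.75 | 2.38 | 1.58 |
| 25% | 10 | 7.50 | 2.51 | 2.99 |
| 50% | 5 | 2.50 | 2.75 | 0.91 |
| 50% | 10 | 5.00 | 2.90 | 1.72 |
| 75% | 5 | 1.25 | 2.38 | 0.53 |
| 75% | 10 | 2.50 | 2.51 | 1.00 |

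**Several doses per patient.** These are simulations with 150 patients per phase, per-patient means, other doses starting at or around the due time, shifts of 5 to 10 minutes and the late share unchanged. The table shows how often the signed t-test was significant at 0.05 (the significance level is also an assumption).

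| Late share | Late doses 30 min + exponential, mean 20; 12 doses | Late doses 30 min + exponential, mean 60; 10 doses, ICC 0.1 |
|---|---|---|
| 25% | 90–100% | 34–91% |
| 50% | 46–93% | 15–39% |
| 75% | 17–47% | 6–14% |

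The first column counts significant improvements only. In those runs a test on the late proportion showed a significant improvement in 1.5–3.6%, about what chance gives, over shifts of 5 to 15 minutes. With the longer tail and ICC 0.3, the signed t-test figures fall to 20–66%, 14–29% and 7–11%.

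**Does absolute deviation alone settle it?** No. With 25% late and a 10-minute shift it worsens from 11.25 to 18.75 minutes if other doses start at the due time. It improves from 22.5 to 15.0 if they start 15 minutes after it (0.25 × 45 + 0.75 × 15 = 22.5; 0.25 × 45 + 0.75 × 5 = 15.0). The late share is the same throughout.

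**Does late share alone settle it?** No. When late doses were simulated falling from about 90 to 45 minutes late with the late share fixed, the late-proportion test was significant in 4–5% of runs, and the signed and absolute tests in 100%.

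**The case against.** The strongest reply is that the plan never says the difference is signed. The wording is neutral, the hypotheses speak only of making a difference, and the tests are two-sided, so no lower signed mean is named as proof of benefit. This stands: a reader might infer that the protocol has chosen a signed measure, and the text does not support that. What remains is that subtraction is the default computation and nothing in the plan prevents it.

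Second, the result needs an assumed behaviour, namely on-time doses moving earlier while late doses do not change. That is also fair. A reader might infer that reminders cease before the due time and so cannot help late doses. The stop rule is ambiguous, and the Rationale describes alerts when the medication is to be given. The documents do not say late doses will stay late; the point is that a signed mean could not show it if they did.

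Third, larger values can be produced by starting the other doses 15 minutes after the due time: z = 4.24 at 25% late with a 10-minute shift, and 5.83 at 15% late. These should not be used as evidence of offsetting. Doses moving from +15 to +5 minutes are never early and end up closer to schedule, which is arguably a real gain.

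Fourth, the only lateness figure in the documents, 75%, lies where the effect is weakest. It counts patients rather than doses, so it does not fix the dose-level share.

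**Conclusion.** The point holds in a conditional form. The timing metric is unspecified, and the most obvious analysis of it could move in the favourable direction with no fewer late doses, because this intervention prompts before the due time. In the one-dose illustration z runs from about 0.5 to 4.1. It exceeds 1.96 at 15% late for either shift and at 25% late for a 10-minute shift, and not at 50% or 75% late. More doses per patient strengthen the effect; right-skewed lateness weakens it. All of these sizes rest on assumed late shares, delays and shifts. The change is worth making before analysis. It concerns one secondary endpoint under secondary objectives 1 and 2, and the primary endpoint is untouched.

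**What to change.** State in Secondary Endpoints and Data Analysis that the signed mean will not be used as evidence of better timeliness. From the barcoding data already planned in both phases, classify each scheduled PD dose as late (more than 30 minutes after due), on time (within 30 minutes, per Appendix E) or early (more than 30 minutes before). Compute the three proportions for each patient, and compare the late proportion between phases with the Wilcoxon test already named. Under this rule a dose given 10 or 15 minutes early is still on time, so it neither earns credit nor hides a late dose.

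Report each patient's absolute deviation in minutes beside the late proportion and interpret the two together, for the reasons shown in the working.

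The cost is a text edit and one more timing summary, with no extra patients, data source or device change. The 30-minute cut discards some information, which the minutes measure retains. For a true 10-point fall in late share (from 25%, 50% or 75%; 10 doses per patient, no shift in other doses), the late-proportion test was significant in 98–100% of simulated trials and the signed t-test in 97–100%. Power is therefore not lost for that kind of improvement, although it would be for late doses that only become less late.

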## **Prospective Study Period**

Data collection starting after completion of the Parkinson's Disease Inpatient Clinical Knowledge and Management Program for staff nurses, advanced practice nurses (APN), nursing assistants, patient care technicians, case managers, adult inpatient physician assistants, pharmacists, occupational therapists, physical therapists, nurse educators, and dietitians.

- Data will be extracted from EPIC and WatchRx records from the Watch Rx Web Interface.

Data collected from the automatic dispensing cabinet barcoding database will verify accuracy and timeliness of medication.

- Unstructured data will be collected by the principle investigator (PI), designees inclusive of study staff through focused chart review on 150 patients.
- Data will be analyzed for objectives and endpoints.

This data will compare prevalence of medication errors, complications associated with administration of contraindicated medications and timing of medications, falls and falls with

injury, positive CAM and Mini-Cog Scores, length of stay and cost per case in the study population. This phase will also assess the knowledge of the clinicians regarding the basic aspects of Parkinson's Disease inpatient management, the Parkinson's Disease Inpatient Clinical Knowledge and management program and integration of the smartwatch into the PD medication management.

- Parkinson's Disease Knowledge Assessment Survey (Appendix A)
- Parkinson's Disease Inpatient Clinical Knowledge and Management Program (Appendix B)

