## **Objectives:**

After participating in educational offerings, the (HackensackUMC employed) target audience will be able to:

1. Describe the pathophysiology of Parkinson's Disease (PD).
2. Discuss the signs and symptoms of PD.
3. Identify the treatment options and medications used to manage patients with PD.
4. Explain the medication contraindications for patients with PD.
5. Explain the importance of administration of PD medications "On Time Every Time."
6. Recognize the complications of not giving PD medications on time

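### The delirium and confusion endpoints count positive scores with no assessment denominator, so a change in screening between phases can create or hide a difference

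*Combined protocol and SAP*

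**What the plan says.** The Protocol Synopsis and the Secondary Endpoints section both list "Number of positive delirium scores" and "Number of positive confusion scores". Neither gives a denominator.

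The definitions table names the CAM as the delirium examination and the Mini-Cog as a dementia examination. No section ties an instrument to confusion by name. The nearest is the Prospective Study Period section, whose list of comparisons includes "positive CAM and Mini-Cog Scores". That list opens with "This data will compare prevalence of medication errors", so it uses the word prevalence, but it does not say of what total.

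Other sections that bear on the point:

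- **Retrospective Study Period:** the 2015 data are extracted from the electronic record, so screening is whatever was charted in routine care.
- **Prospective Study Period:** record extraction is supplemented by chart review of 150 patients for unstructured data.
- **Measurements:** no CAM or Mini-Cog item is listed, whether result, date or number of assessments.
- **Data Analysis:** two-sided t or Wilcoxon tests for continuous variables between independent groups (ANOVA or Kruskal-Wallis where relevant), and Fisher or chi-square tests for categorical ones. There is no rate model, offset or missing-data rule.
- **Sample Size Calculation:** a convenience sample of 150 patients per phase.

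**The concern.** A count of positive scores depends on how often patients have delirium or confusion, on how many patients are tested, and on how many times each is tested. The plan records only the product. A patient tested repeatedly can add several positives, one tested once can add at most one, and one never tested adds none. Read literally, the count does not separate a patient who tested negative from one who was not tested.

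The two phases are years apart and draw on different data collection. Nothing in the plan requires equal screening, and nothing legible in it would show afterwards whether screening was equal. A difference in these two endpoints could therefore reflect testing practice, and an absence of difference could hide a real change. Using the same record system in both phases does not help, because it does not equalise who was tested. Dividing by patient-days would not help either, because testing per day may also differ.

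**Working it through.** The plan gives no delirium rate, screening rate, alpha or power, so there is no stated figure to reproduce.

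**Inputs from the documents.** 150 patients per phase; two-sided tests.

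**Assumed inputs.** Alpha 0.05 and every rate, coverage, screening frequency and correlation below. In examples 1 to 3 the true positive rate is the same in both phases.

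**1. Coverage differs, one assessment per patient.** Apparent rate = prevalence × coverage, with unassessed patients contributing no positives.

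- Prevalence 20%, coverage 50% against 90%: 0.20 × 0.50 = 10% and 0.20 × 0.90 = 18%, or 15 of 150 against 27 of 150 expected.
- Chi-square on 15 against 27: pooled rate 42/300 = 0.14; z² = 0.08² / (0.14 × 0.86 × 2/150) = 3.99, p = 0.046. Fisher's exact test, which the plan also allows, gives p = 0.066. One expected table is therefore borderline, and the rejection rate over repeated trials is the better measure.
- Rejection rate = Φ[(|p1 − p0| − 1.96 × SE0) / SE1]. SE0 = √(2 × 0.14 × 0.86/150) = 0.0401 and SE1 = √((0.10 × 0.90 + 0.18 × 0.82)/150) = 0.0398. This gives about 0.515, or 52%.
- Coverage 70% against 90%: 14% against 18%, rejection 15.5%. Coverage 50% against 70%: 10% against 14%, rejection 18.5%.

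**2. Frequency differs, everyone assessed.** Mean count = p × k, and P(any positive) = 1 − (1 − p)^k, for k independent assessments with positive rate p.

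- p = 10%, k = 2 against 4: mean count 0.20 against 0.40. P(any positive) is 1 − 0.9² = 19.0% against 1 − 0.9⁴ = 34.4%. A test on any positive rejects in 86% of trials.
- p = 10%, k = 3 against 4: 27.1% against 34.4%, rejection 28%.

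**3. Counts tested as the plan allows.** A simulation (4,000 runs per scenario, within-patient correlation 0.3, number of assessments varying between patients) compared a Wilcoxon test on raw counts with positives divided by assessments, using patient-clustered variance.

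| Mean assessments per assessed patient | Positive rate | Coverage | Wilcoxon on counts | Positives per assessment |
|---|---|---|---|---|
| 2 v 2 | 10% | all | 5.0% | 4.8% |
| 3 v 4 | 10% | all | 12.7% | 5.0% |
| 2 v 4 | 5% | all | 24.2% | 5.0% |
| 2 v 2 | 10% | 60% v 90% | 25.4% | 5.8% |
| 2 v 4 | 10% | all | 47.2% | 5.6% |
| 3 v 6 | 10% | all | 50.4% | 5.5% |
| 2 v 4 | 20% | all | 79.9% | 5.3% |
| 2 v 4 | 10% | 60% v 90% | 83.4% | 6.0% |

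The last column stays near 5% because the simulation makes testing independent of a patient's own risk. Testing prompted by suspicion would break that.

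**4. Masking.** If the true rate per assessment halves from 20% to 10% while assessments double from 2 to 4, the mean counts are 0.20 × 2 = 0.40 and 0.10 × 4 = 0.40. A real improvement disappears.

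**The case against.** Four points can fairly be made for the plan.

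*The plan speaks of prevalence, so a proportion may be intended.* That is possible. But the wording names no denominator and does not match the endpoint list. Even a proportion of all 150 patients would leave the coverage problem of example 1.

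*Nothing shows that screening will change.* This stands. A reader might infer that the Program raises screening, so that better vigilance would be reported as more delirium. The documents do not support that. The relevant learning objective is "Recognize the complications of not giving PD medications on time", which concerns late medication, and Appendix B does not mention CAM, Mini-Cog or delirium screening. Screening could rise, fall or stay the same. The exclusion of disoriented patients who cannot follow commands would also tend to lower prospective counts if it is not applied to the 2015 charts.

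*The plan does not say unscreened patients score zero.* Also correct. It is silent. Zero is only what a literal count yields, and a missing-data rule would change it. Repeat testing at each shift is likewise not described for either instrument.

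*The field may exist.* The Measurements list names no CAM or Mini-Cog result at all, so it is probably not the whole extract, and the Appendix F tool is legible only in part. A column for assessments cannot be ruled out. It would not change how the endpoints are defined.

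**Conclusion.** The concern holds in a conditional form. As defined, both endpoints move with screening as well as with patient outcome, and the planned unadjusted tests cannot separate the two. With no true change, the illustrations give a false difference in about 16% to 52% of trials for the coverage gaps shown, and in 12.7% to 83.4% of simulated trials on raw counts when screening rose. All of these rest on assumed rates, coverage, frequencies, correlation and alpha. With equal screening the simulated rate was 5.0%.

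The direction of any bias is unknown, and a claim that the Program will appear to cause delirium goes beyond the text. These are two of seven secondary endpoints in a study whose primary endpoint is clinician knowledge, so this is a change that should be made, but it does not threaten the primary result.

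**What to change.** - Extract the number and dates of CAM and Mini-Cog assessments, with results, in both phases.
- Define each endpoint as positive assessments divided by assessments done, with patient-clustered variance, or use a count model with assessments as offset.
- Treat never-assessed patients as missing, not zero.
- Report by phase the percentage of patients assessed and assessments per patient-day.
- Give any positive among patients assessed only as a supporting analysis, using at most one assessment per patient per day. It should not be the main endpoint, because it still rises with repeat testing (19.0% to 34.4% in example 2).
- State which instrument defines confusion, and align the Synopsis and Secondary Endpoints wording with the prevalence wording in the Prospective Study Period section.

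The cost is a few extra extract fields and some analysis-plan wording. The 2015 denominator will shrink if many patients were never assessed. If 2015 testing was prompted by suspicion, the rate among those assessed will be too high for that phase. No denominator cures that, so it should be stated as a limitation.
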